11.3 Data Management and Monitoring/Auditing

As has been done previously for the phase 1 study of acalabrutinib (13), adverse events will be monitored throughout treatment and toxicities will be assessed using the National Cancer Institute Common Toxicity Criteria for AEs, with its latest version, currently version 4.03.

11.4 Adherence to the Protocol

Except for an emergency situation in which proper care for the protection, safety, and well-being of the study subject requires alternative treatment, the study shall be conducted exactly as described in the approved protocol.

11.4.1 Emergency Modifications

Investigators may implement a deviation from, or a change of, the protocol to eliminate an immediate hazard(s) to trial subjects without prior IRB approval. For any such emergency modification implemented, an IRB modification form must be completed within five (5) business days of making the change.

11.4.2 Other Protocol Deviations/Violations

All other planned deviations from the protocol must have prior approval by the Principal Investigator and the IRB. According to the IRB, a protocol deviation is any unplanned variance from an IRB approved protocol that:

- Is generally noted or recognized after it occurs
- Has no substantive effect on the risks to research participants
- Has no substantive effect on the scientific integrity of the research plan or the value of the data collected
- Did not result from willful or knowing misconduct on the part of the investigator(s).

An unplanned protocol variance is considered a violation if the variance:

- Has harmed or increased the risk of harm to one or more research participants.
- Has damaged the scientific integrity of the data collected for the study.
- Results from willful or knowing misconduct on the part of the investigator(s).
- Demonstrates serious or continuing noncompliance with federal regulations,
 State laws, or University policies.

If a deviation or violation occurs without prior approval from the Principal Investigator, please follow the guidelines below:

Protocol Deviations: Deviations should be summarized and reported to the IRB at the time of continuing review.

Protocol Violations: Study personnel should report violations within two (2) week of the investigator becoming aware of the event using the same IRB online mechanism used to report Unanticipated Problems.

11.5 Amendments to the Protocol

Should amendments to the protocol be required, the amendments will be originated and documented by the Principal Investigator. It should also be noted that when an amendment to the protocol substantially alters the study design or the potential risk to the subject, a revised consent form might be required. The written amendment, and if required the amended consent form, must be sent to the IRB for approval prior to implementation.

11.6 Confidentiality

The specimens will be coded and data will be stored in the Allergy-Immunology Research Labs, Mezzanine, McGaw Pavilion, or in locked file cabinets and/or on password protected computers. Only the study personnel will have access to the specimens and data generated. The PI and the study team members will be responsible for receipt or transmission of the data and specimens. The specimens will be maintained until exhausted or until the study ends. If there are remaining samples at the end of the study, any identifying information will be removed from the sample vial and the specimens will be treated with 10% bleach and discarded per standard practice. Unused portions of the specimens may be shared with other members of the University community. The original data will remain with the PI in the Allergy Division. No PHI will be shared.

11.7 **Provisions to Protect the Privacy Interests of Subjects**

Certain other people besides the PI and his research team may review the results of the study, such as administrative staff members from the Office of Research, Office of Research Integrity and members of the Institutional Review Board, and members of the Office for Human Research Protections. There is a slight risk that a subject's privacy might be at risk. All of the above mentioned people in the respective capacities are obligated to protect a subject's privacy and have training and certification in the safeguarding of the patient's privacy. All data and results will be maintained in the Allergy-Immunology Research Labs, Mezzanine, McGaw Pavilion, in locked file cabinets and/or on password protected computers.

To help the subjects feel at ease, these safeguards are outlined in the consent form.

As far as information in medical records, only licensed medical personnel would have permission to access the information.

11.8 **Record Retention**

Study documentation includes all Case Report Forms, data correction forms or queries, source documents, Sponsor-Investigator correspondence, monitoring logs/letters, and regulatory documents (e.g., protocol and amendments, IRB correspondence and approval, signed subject consent forms).

Source documents include all recordings of observations or notations of clinical activities and all reports and records necessary for the evaluation and reconstruction of the clinical research study.

Government agency regulations and directives require that the study investigator must retain all study documentation pertaining to the conduct of a clinical trial. In the case of a study with a drug seeking regulatory approval and marketing, these documents shall be retained for at least two years after the last approval of marketing application in an International Conference on Harmonization (ICH) region. In all other cases, study documents should be kept on file until three years after the completion and final study report of this investigational study.

11.9 **Obligations of Investigators**

The Principal Investigator is responsible for the conduct of the clinical trial at the site in accordance with Title 21 of the Code of Federal Regulations and/or the Declaration of Helsinki. The Principal Investigator is responsible for personally overseeing the treatment of all study subjects. The Principal Investigator must assure that all study site personnel, including sub-investigators and other study staff members, adhere to the study protocol and all FDA/GCP/NCI regulations and guidelines regarding clinical trials both during and after study completion.

The Principal Investigator at each institution or site will be responsible for assuring that all the required data will be collected and entered onto the Case Report Forms. Periodically, monitoring visits will be conducted and the Principal Investigator will provide access to his/her original records to permit verification of proper entry of data. At the completion of the study, all case report forms will be reviewed by the Principal Investigator and will require his/her final signature to verify the accuracy of the data.

Appendix 1: Pill Diary

		монтн				
Sunday	Monday	Tuesday	Wednesday	Thursday	Friday	Saturday
Н	4					
-						L
		L				L

The study coordinator will fill in the month and days.

Please document number of pills and time you took the ibrutinib.

STATISTICAL ANALYSIS PLAN

Study Design and Endpoints

This is an open label study of acalabrutinib in 10 food-allergic adults to determine the effect of pretreatment (100 mg twice daily for 4 doses total) with acalabrutinib on food allergen reactivity in foodallergic subjects. There are 3 planned study visits where endpoint assessments will be collected. The primary endpoint will be assessed at Visit 1 (baseline) and Visit 2 (after acalabrutinib). Secondary and exploratory endpoints will be assessed at Visits 1, 2, and 3 (follow-up).

Primary endpoint: Change in subjects' threshold dose of peanut protein to elicit an objective clinical reaction

Secondary endpoints:

- 1. Change in size of skin prick test wheal
- 2. Change in percent of ex vivo basophil activation to anti-IgE and peanut, as determined by CD63 expression

Safety considerations and toxicity monitoring: Laboratory testing (complete blood counts, serum chemistries) and electrocardiogram

Given the nature of the study, it will be stopped if >50% of patients have a DLT as described in the protocol.

Sample Size and Power Analysis

Sample size was calculated based on the primary endpoint, assuming that the difference in threshold from baseline to after acalabrutinib is normally distributed with a standard deviation of 1.1 natural log units. Therefore, 10 subjects allows for 80% power to detect a 3-fold increase (1.1 natural log units; i.e. 1 food dose escalation) in the threshold food dose, using a paired t test with p<0.05 as an approximation. though non-parametric tests will be utilized in the final analysis if needed.

Data Analysis

As this is an open label trial, each subject's responsiveness will be examined compared to themselves (at baseline) prior to initiation of treatment. Descriptive statistics will be used to analyze endpoints. The primary endpoint will be analyzed by log transformation and paired t test with p value < 0.05, if appropriate. If assumptions for paired t test are violated, a Wilcoxon non-parametric sign test will be used.

Secondary endpoints will be analyzed using ANOVA with repeated measures across all visits with p value < 0.05. For experiments with multiple dosing levels, we will first examine if there is a dose-level by treatment interaction. If there is an interaction, treatment effects in individual dosing levels will be examined. Non-parametric tests will be utilized in place of ANOVA if necessary. Corrections will be made for multiple comparisons, if applicable, using a Šídák or Bonferroni multiple comparisons correction with an alpha threshold of 0.05.

For safety endpoints, ANOVA will be used for analysis of individual laboratory values (blood counts or chemistries).

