At Visit 1, after undergoing informed consent, subjects will undergo procedures for assessment of baseline status and eligibility (clinical history and skin prick test ISPT) to peanut and/or tree nuts as well as histamine and saline SPT positive and negative controls, respectively). After eligibility is confirmed, subjects will undergo a single-blind, placebo-controlled graded food challenge (SBPCFC) of up to 4 g of peanut or tree nut protein, administered over escalating doses while being monitored in a clinical research unit (CRU) setting. Prior to the SBPCFC, 30 mL of peripheral blood will be collected for basophil activation testing (BAT), serum specific IqE to peanut/tree nuts and components, as well as toxicity lab testing monitoring. During the food challenge, subjects will be assessed for signs and symptoms of foodinduced anaphylaxis between each dose per food challenge protocol, upon report of any symptoms and should any objective change in clinical status occur. Once a confirmed reaction occurs, the food challenge will be terminated and the reaction treated until it has resolved. Subjects will be discharged from the CRU no sooner than 2 hours after completion of the food challenge. They may be observed longer should a reaction occur at the investigator's discretion. Additional blood will be drawn at fixed intervals for biomarkers of anaphylaxis including mast cell and basophil microparticle analysis. This visit will establish each subject's baseline threshold dose for peanut/tree nut reactivity.

After a minimum of a two-week recovery period, subjects will be given acalabrutinib (four doses of 100 mg of acalabrutinib to be taken orally twice daily) and return for Visit 2 to undergo repeat SPT, SBPCFC, and phlebotomy in an identical manner to Visit 1 to establish each subject's new threshold dose for peanut/tree nut reactivity while on acalabrutinib, which we hypothesize will be higher. At this point of the protocol, acalabrutinib dosing will be stopped. Follow up visits for up to 6 months after cessation of acalabrutinib will be conducted to repeat toxicity labs and skin testing.

At each visit, subjects will be monitored for toxicities, including CBC w/diff, CMP, and pregnancy testing. Prior to drug initiation and at the end of the trial, an EKG will be performed.

STUDY SUMMARY

Title	Preventing Life-Threatening Allergic Reactions with Acalabrutinib, an FDA-Approved BTK Inhibitor			
Protocol Number	MD12042018			
Phase	Phase 2			

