3.3 Study Stopping Criteria

The study will be stopped if 2 or more subjects experience a serious adverse event, excluding adverse events that would be expected within the context of skin testing or oral food challenge, including medical treatment of clinical reactions during food challenge. Toxicities (section 4.2) and adverse events (section 7.0) are listed below. Monitoring is described in section 8.0.

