4.0 TREATMENT PLAN

4.1 **Treatment Dosage and Administration**

Prior studies in food-allergic subjects suggest that two standard (420 mg) doses (two days) of ibrutinib, an irreversible BTK inhibitor, are sufficient to completely inhibit BAT and suppress food SPT wheal size by an average of 77% (44% of all food SPTs became negative) (16). Additional doses of ibrutinib (up to 7 days) did not offer further suppression of SPTs, and BAT remained completely abolished for the duration of treatment. Therefore, we propose to extend these findings to acalabrutinib, another selective irreversible BTK inhibitor. Ten subjects will take acalabrutinib 100 mg twice daily by mouth (every 12 hours) for 2 days. Each subject will be enrolled for a minimum of 3 months (including the follow-up visit for toxicity monitoring).

Acalabrutinib is approved as a daily medication for another indication, and we propose to use the drug in adults only at its approved oral dosing of 100 mg twice daily for a maximum of two days. Dose limiting events include grade 3 or 4 hematologic events, grade 3 or 4 hepatotoxicity, AST or ALT >3 times normal range, creatinine > 2.5 times normal range. Dose-limiting toxicity (DLT) evaluation will be performed throughout the study.

The capsules should be swallowed intact with water. Subjects should not attempt to open capsules or dissolve them in water. Acalabrutinib can be taken with or without food.

If a dose is missed, it can be taken up to 3 hours after the scheduled time with a return to the normal schedule with the next dose. If it has been > 3 hours, the dose should not be taken and the subject should take the next dose at the scheduled time. The missed dose will not be made up and must be returned to the site at the next scheduled visit.

In healthy volunteers, co-administration with CYP3A inhibitors increased C_{max}, and therefore the drug will not be concomitantly administered with strong inhibitors or inducers of CYP3A.

4.2 **Toxicities and Dosing Delays**

Although toxicity is not expected given that subjects will only receive two days of drug, any subject who receives treatment on this protocol will be evaluable for toxicity. Each subject will be assessed for the development of toxicity according to the Time and Events table (Section 5.4).

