At each visit, subjects will be monitored for toxicities. This study will follow the FDA Guidance For Industry ("Toxicity grading scale for healthy adult and adolescent volunteers enrolled in preventative vaccine clinical trials") grading system for adverse events (17). If a subject develops a grade 3 or 4 nausea, vomiting, diarrhea, hematologic toxicity, renal toxicity, or hepatotoxicity, or any other Grade 4 toxicity or unmanageable Grade 3 toxicity, the medication will be stopped. Protocols for specific toxicities are listed below.

Hematological Toxicities: ANC < 1,500/µL or platelets < 100,000/µL will result in discontinuation of protocol therapy.

Renal Toxicity: Creatinine will be monitored per protocol. Creatinine levels >2.5 times the normal limit will result in discontinuation of protocol therapy.

Hepatotoxicity: Grade 3 hepatotoxicity, or an increase in AST or ALT >3 times upper limit of normal, will result in discontinuation in protocol therapy.

4.3 **Concomitant Medications/Treatments**

At the systemic exposure levels expected in this study, acalabrutinib inhibition of CYP metabolism is not anticipated.

However, acalabrutinib is metabolized by CYP3A. Concomitant administration of acalabrutinib with a strong CYP3A and P-glycoprotein (P-gp) inhibitor, itraconazole increased exposure by approximately 5-fold. Conversely, concomitant administration of acalabrutinib with a strong CYP3A inducer, rifampin, decreased acalabrutinib exposure and could reduce efficacy. Consequently, the concomitant use of strong inhibitors/inducers of CYP3A should be avoided when possible.

If medically justified, subjects may be enrolled if such inhibitors or inducers can be discontinued or alternative drugs that do not affect these enzymes can be substituted within 7 days before first dose of study drug.

The effect of agents that reduce gastric acidity (eg. proton pump inhibitors or antacids) on acalabrutinib absorption was evaluated in a healthy volunteer study (ACE-HV-004). Results from this study indicate that subjects should avoid the use of calcium carbonate containing drugs or supplements for a period of at least 2 hours before and at least 2 hours after taking acalabrutinib. Use of omeprazole, esomeprazole, lansoprazole or any

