other proton pump inhibitors while taking acalabrutinib is not recommended due to a potential decrease in study drug exposure. However, the decision to treat with protonpump inhibitors during the study is at the investigator's discretion, with an understanding of the potential benefit to the subject's gastrointestinal condition and a potential risk of decreased exposure to acalabrutinib.

Although the effect of H2-receptor antagonists (such as famotidine or ranitidine) on acalabrutinib absorption has not been evaluated, if treatment with an H2-receptor antagonist is required, the H2-receptor antagonist should be taken approximately 2 hours after an acalabrutinib dose.

The following concomitant medications/treatments are not allowed: immunomodulatory therapies, oral corticosteroids within 1 month of study participation; those taking antihistamines must stop these drugs for one week prior to enrollment and must refrain from taking antihistamines during the duration of the study so as not to interfere with SPT responses; and any other prior investigational interventions in the past 6 months.

4.4 **Duration of Therapy**

Treatment will last for 2 days. Reasons the study medication may be discontinued include:

- Intercurrent illness that prevents further administration of treatment;
- Unacceptable adverse event(s);
- Subject decides to withdraw from the study; or
- General or specific changes in the subject's condition render the subject unacceptable for further treatment in the judgment of the investigator.

4.5 **Duration of Follow Up**

Subjects will be followed for 30 days after cessation of acalabrutinib treatment. Subjects will be removed from the rapy when any of the criteria listed in Section 5.5 apply. The Principal Investigator will be notified. The reason for study removal and the date the subject was removed will be documented in the Case Report Form. Subjects removed from treatment for unacceptable adverse events will be followed until resolution or stabilization of the adverse event.

4.6 **Subject Replacement**

Subjects who withdraw voluntarily from the study, but were tolerating the drug will be replaced. Subjects who drop out or miss doses due to toxicity will not be replaced since these subjects will be considered to have experienced a dose limiting toxicity.

5.0 **STUDY PROCEDURES**

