10.1 Study Design/Study Endpoints

This is an open label study of acalabrutinib in 10 food-allergic adults to determine the effect of pretreatment with acalabrutinib on food allergen reactivity in food-allergic subjects given acalabrutinib 100 mg twice daily for 2 days. The primary endpoint is the threshold dose of food at which a subject reacts before (at baseline) and after acalabrutinib therapy. Given the nature of the study, it will be stopped if 2 or more patients have a DLT.

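### The SAP stops the study when more than half of patients have a DLT; protocol 10.1 stops it at two, so the rules disagree at 2 to 5 DLTs in the planned 10.

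*Combined protocol and SAP*

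**What the plan says.** Two current texts give a study-level stop for dose-limiting toxicity (DLT).

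- Protocol 10.1: "Given the nature of the study, it will be stopped if 2 or more patients have a DLT".
- SAP, Study Design and Endpoints: the sentence opens with the same phrase, then says "it will be stopped if >50% of patients have a DLT as described in the protocol".

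Related provisions:

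- Protocol 4.1 defines DLTs as grade 3 or 4 hematologic events, grade 3 or 4 hepatotoxicity, and "AST or ALT >3 times normal range, creatinine > 2.5 times normal range".
- Protocol 4.6 adds subjects who drop out or miss doses because of toxicity: "these subjects will be considered to have experienced a dose limiting toxicity". It also replaces voluntary withdrawals who were tolerating the drug.
- Protocol 3.3, repeated in 8.3.3, has a separate rule: "The study will be stopped if 2 or more subjects experience a serious adverse event". Events expected from skin testing or food challenge are excluded.
- Protocol 11.4 requires that, emergencies aside, "the study shall be conducted exactly as described in the approved protocol".

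**The concern.** The SAP cites the protocol as its source but states a threshold that the protocol does not contain. The cross-reference can supply the definition of a DLT; it cannot supply a majority rule. The SAP also does not say what the percentage is taken of: planned, treated so far, or evaluable patients. Because 4.6 allows replacement, the number treated need not be 10.

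At stake is whether the study stops after a second DLT. Anyone who checks the stopping rule from the SAP alone, during the study or in the report, would record it as not met at 2 to 5 DLTs.

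The subject-level discontinuation limits in 4.2 do not fill this gap for laboratory DLTs. The first scheduled on-drug laboratory tests are at Visit 2, on the second day of treatment (5.2.1 and 5.2.2), and the Study Schema says of that visit: "At this point of the protocol, acalabrutinib dosing will be stopped". By then there is almost no dosing left to withhold from that subject. For non-serious laboratory toxicity, the study-level rule is the one that protects later subjects.

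**Working it through.** Neither document derives its DLT threshold, so there is no stated figure to reproduce on this point.

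**Inputs.** Planned N = 10 (protocol 4.1 and 10.1; SAP). Protocol threshold: at least 2 patients (10.1). SAP threshold: more than 50% of patients. The documents give no DLT rate *p*, and 4.2 says toxicity is not expected. The rates below are therefore assumptions, with patients treated as independent and at equal risk.

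**Step 1: the SAP threshold as a count.** 5/10 = 50% is not more than 50%; 6/10 = 60% is. With 10 as denominator the SAP rule needs at least 6 DLTs. The rules disagree at 2, 3, 4 and 5.

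**Step 2: how often they disagree, denominator 10.** Let X ~ Binomial(10, p). The protocol rule is met with probability P(X ≥ 2) = 1 − (1−p)^10 − 10p(1−p)^9. The SAP rule is met with probability P(X ≥ 6). The difference is the chance that only the protocol rule is met.

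Example at p = 0.10: 1 − 0.3487 − 0.3874 = 0.2639.

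| Assumed DLT rate | Protocol rule met | SAP rule met | Only protocol rule met |
|---|---|---|---|
| 1% | 0.4% | <0.001% | 0.4% |
| 5% | 8.6% | <0.001% | 8.6% |
| 10% | 26.4% | 0.015% | 26.4% |
| 20% | 62.4% | 0.6% | 61.8% |
| 30% | 85.1% | 4.7% | 80.3% |

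**Step 3: the percentage read as a running count.** If the denominator is the m patients treated so far, the smallest count above 50% is floor(m/2) + 1. For m = 1 to 10 that is 1, 2, 2, 3, 3, 4, 4, 5, 5, 6. On this reading the SAP is stricter than the protocol at m = 1, agrees at m = 2 and 3, and is looser from m = 4 on. Enumerating all 2^10 outcome sequences gives:

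| Assumed DLT rate | Running SAP rule ever met | Protocol rule met, SAP rule never met |
|---|---|---|
| 1% | 1.0% | 0.3% |
| 5% | 5.3% | 6.5% |
| 10% | 11.1% | 19.2% |
| 20% | 24.8% | 40.3% |
| 30% | 41.2% | 45.1% |

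Much of the first column comes from stopping at 1 of 1. Counting only from the second patient onward, the running rule is met in 0.03%, 0.8%, 3.1%, 12.8% and 28.6% of trials.

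**Step 4: does the serious-event stop cover the gap?** It covers only DLTs that are also serious under 8.1.3. A transaminase above 3 times or a creatinine above 2.5 times the normal range, or a dose missed for toxicity, need not be serious. The probabilities in Steps 2 and 3 count every DLT, including any that would also be serious. They are therefore upper bounds on the part that the serious-event rule leaves open.

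**The case against.** The strongest case on the other side is that no harm follows. Protocol 11.4 binds conduct to the protocol, monitoring is described in protocol section 8.0, and the documents describe no safety board working from the SAP. Stopping at the earlier trigger satisfies both rules, so a trial run as required stops at two DLTs. This stands as a limit on the practical consequence. It does not make the SAP sentence correct.

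Second, neither document says which prevails if they differ, so calling the SAP figure the wrong one is an inference. That is true, but the inference is strong: the SAP refers to the protocol as its source, and the protocol governs conduct.

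Third, the serious-event stop overlaps. Grade 4 is defined in 8.1.2 as risk of death, and life-threatening events are serious under 8.1.3.2, so grade 4 DLTs already count towards the stop at two. Investigator judgement may bring in some grade 3 events. This narrows the gap to non-serious DLTs but does not close it.

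Fourth, the higher assumed rates have no support in the documents. Exposure is four doses, entry requires normal liver and renal tests, and the earlier study of up to 7 days of ibrutinib reported no toxicity. This also stands: at a 1% rate the rules disagree in only 0.4% of trials.

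Fifth, 10 is the natural denominator, since that SAP section opens with it. That may be so, but on that reading the discrepancy is at its widest.

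**Conclusion.** The SAP sentence is wrong as written. It states a study-level safety threshold of at least 6 in the planned 10, where the protocol it cites says 2, and it leaves the denominator open. The disagreement at 2 to 5 DLTs is a matter of arithmetic and needs no assumption beyond a denominator of 10. On a running denominator the rules still differ, in both directions.

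How often this would matter depends on a DLT rate that the documents do not give. The chance that only the protocol rule is met runs from 0.4% at an assumed 1% rate to 26.4% at 10% and 80.3% at 30%, with all 10 treated and independent risks. The true rate may well be low, and 11.4 gives a correct basis for stopping at two. The correction should still be made: a safety stop must have a single value, and the intended one is already in the protocol.

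**What to change.** Replace the SAP sentence with the protocol 10.1 rule, for example: *The study stops once two patients have had a DLT as defined in protocol 4.1, counting drop-outs and missed doses due to toxicity (4.6), whatever number has been treated. The separate stop for serious adverse events in protocol 3.3 and 8.3.3 also applies.* A count removes the need for a denominator.

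The cost is one sentence in the SAP, with no change to data, patients or procedures. If a majority rule was in fact intended, that would change protocol 10.1. It would need an amendment under 11.5, with the denominator and the time of assessment stated in both documents.

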1.3 Rationale

There are currently no treatments for food allergy. IgE uniquely arms mast cells and basophils via their surface expression of FcεRI, and when cross-linked by allergens, causes mediator release that then results in an allergic reaction. Crosslinking of the receptor is known to activate a number of kinases. BTK is a key component of FcɛRI signaling and activation of mast cells and

basophils. Since signaling mediated by FcɛRl aggregation is thought to require the activity of BTK (8.9), [name] et. al. was the first to test ibrutinib, a first generation BTK inhibitor, for its ability to prevent FcɛRI activation of human basophils in vitro (9). Ibrutinib inhibited IqE-mediated CD63, CD203c and CD11b upregulation, and release of histamine, LTC4 and IL-4 as well as the cytosolic calcium response (IC₉₀ of ≈50 nM). Ibrutinib did not inhibit basophil activation by fMLP or C5a and did not inhibit IL-13 release induced by IL-3, suggesting that BTK is required for IgEmediated activation, but not IqE-independent activation, of human basophils (12). We recently completed an open label trial to test the hypothesis that ibrutinib would abrogate IqE-mediated BAT and food SPT responses in peanut and tree nut allergic adults (11). We found that 2 doses of ibrutinib significantly reduced SPT wheal and flare area (77 and 86% reductions, respectively; overall, 44% of SPTs became negative). Additional doses up to 7 days did not demonstrate further suppression compared to 2 days. Anti-IgE induced BAT became negative in all subjects after 2 doses and remained negative during treatment. The vast majority of SPTs and BAT returned to baseline within 1 week of cessation of ibrutinib. No toxicity from treatment was observed, and ibrutinib was well-tolerated by subjects.

We now propose to extend these promising findings in a subsequent open label study using acalabrutinib, a second generation BTK inhibitor, to investigate its ability to prevent clinical allergic reactions to oral food challenge. Because acalabrutinib is more selective for BTK with fewer off-target effects, it has a more favorable safety profile (13).

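### The skin-test and basophil endpoints are tested by a three-visit ANOVA that includes the off-drug follow-up, and the SAP names no Visit 2 versus Visit 1 contrast, the only one that measures the drug effect

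*Combined protocol and SAP*

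**What the plan says.** For skin-prick wheal size and percent basophil activation (CD63), the SAP's Data Analysis section says: "Secondary endpoints will be analyzed using ANOVA with repeated measures across all visits", at the 0.05 level. The SAP's design section places these assessments at Visits 1, 2 and 3. On multiplicity the SAP says "Corrections will be made for multiple comparisons, if applicable", by Šídák or Bonferroni. It allows an unnamed non-parametric substitute for the ANOVA. It names no contrast of interest, family of comparisons, error term (pooled or contrast-specific) or sphericity correction.

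The question itself is narrower. Protocol 2.1.1 asks whether a short course of drug reduces skin-test reactions. The SAP takes each subject's own pre-treatment baseline as the reference. Visit 3 comes after dosing has stopped: 30 days after Visit 2 in the Time and Events table, 3 months after cessation in section 5.3. Section 1.3 reports from the earlier ibrutinib study that "Anti-IgE induced BAT became negative in all subjects after 2 doses", and that most skin-test and basophil results were back at baseline within a week of stopping.

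The primary endpoint, by contrast, has a paired Visit 1 to Visit 2 test.

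**The concern.** A three-visit omnibus F test asks whether any of the three visit means differ. A drift at the off-drug follow-up can make it significant with no drug effect at all. To get from a significant F to a statement about the drug, the analyst must go on to pairwise tests, and the SAP does not say which ones, with what correction or with what standard error. If all three pairs are corrected for, two comparisons that do not measure efficacy use up part of the alpha for the one that does. If a pooled error term is used, the standard error for Visit 2 minus Visit 1 also depends on how variable Visit 3 is.

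At stake is how clearly the skin-test and basophil results can be read. Skin-test suppression also appears in the primary objective, although the endpoint list ranks it as secondary. In an open-label study of 10 subjects it is better not to leave the choice of contrast and error term until the data are in. The timing of Visit 3 differs between sections, which is a further reason not to let the efficacy p-value depend on it.

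**Working it through.** **Inputs from the documents.** The SAP's sample-size section states "10 subjects allows for 80% power to detect a 3-fold increase" in threshold dose, with the difference "normally distributed with a standard deviation of 1.1 natural log units", "using a paired t test with p<0.05 as an approximation". That is n = 10, difference 1.1, SD 1.1 and alpha 0.05. Sidedness is not stated.

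**Assumptions.** The documents give no SD, effect size or visit correlation for the skin test or the basophil test. I borrow the primary endpoint's ratio, 1.1/1.1 = 1 SD of the paired difference, and then vary it.

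**1. The plan's own figure.** Noncentrality = √10 × 1 = 3.162; df 9; two-sided critical t = 2.262. Power = 80.3%. The stated 80% reproduces as a two-sided test (one-sided would give 89.8%).

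**2. Visit 2 minus Visit 1 at 1 SD, by correction.** Same noncentrality, alpha = 0.05/m. The pooled column uses the ANOVA error (df 18) and assumes sphericity.

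| Comparisons m | Own SD (df 9) | Pooled error (df 18) |
|---|---|---|
| 1 | 80.3% | 84.8% |
| 2 | 68.2% | 75.7% |
| 3 | 60.4% | 69.6% |

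**3. Sensitivity to effect size (own SD).** Uncorrected versus Bonferroni for three: 94% versus 82% at 1.25 SD; 99% versus 94% at 1.5 SD; 100% versus 99.8% at 2 SD.

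**4. The omnibus F.** λ = n Σ(μ − mean μ)² / σ²ₑ. With equal variances, visit correlation 0.5 and a paired-difference SD of 1, σ²ₑ = 0.5. Critical F(2, 18) = 3.555.
- Drug effect of 1 SD, Visit 3 fully back to baseline (0, 1, 0): sum of squares 0.667, λ = 10 × 0.667/0.5 = 13.3, power 86.0%.
- Visit 3 only half-way back (0, 1, 0.5): sum of squares 0.5, λ = 10, power 74.2%.
- No drug effect, only Visit 3 shifts by 1 SD (0, 0, 1): λ = 13.3 again, so it rejects 86.0% of the time.

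The first and third patterns have the same λ, so the F test cannot tell them apart.

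**5. Type I error under a true null** (simulation, n = 10, 200,000 trials per pattern).

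| Pattern | Omnibus F, no sphericity correction | Pooled V2−V1, uncorrected | Pooled V2−V1, Bonferroni for 3 |
|---|---|---|---|
| Sphericity | 5.1% | 5.0% | 1.7% |
| Visit 2 SD 1.5 times the others | 5.3% | 6.6% | 2.5% |
| Visit 2 SD 3 times | 7.3% | 9.7% | 4.3% |
| Visit 2 SD 5 times | 8.4% | 11.0% | 5.2% |
| V1–V3 correlation 0.9, Visit 2 correlated 0.1–0.3 | 7.7–8.0% | 10.2–10.6% | 4.6–4.9% |
| Correlation decays with time (V1–V2 0.9, V2–V3 0.85, V1–V3 0.8) | 5.6% | 2.0% | 0.5% |
| Visit 3 SD 2 times the others | 6.0% | 0.9% | 0.2% |

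The paired test with its own SD stays at 5.0%, to within simulation error, in every pattern. When Visit 3 is the noisy visit (SD 1.5, 2 or 3 times the others), the pooled Bonferroni-for-three test has 53%, 34% or 10% power at 1 SD. With Greenhouse-Geisser the omnibus error stays between 4.1% and 5.1% in the unequal-variance patterns.

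**The case against.** The case for leaving the SAP alone is substantial.

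- **The SAP does not prescribe the harmful procedure.** It does not call for three pairwise tests, a correction factor of 3 or pooled error. Correction applies only where applicable, and two comparisons against baseline, or one, would fit the text equally well. This stands. The power figures are therefore conditional on what the analyst chooses.
- **A reader might infer that the plan both loses power and inflates false positives.** The documents do not support that. The power loss needs the correction, and the 10% error needs its absence. With Bonferroni for three, the pooled Visit 2 minus Visit 1 error stays at about 5% or below even in the adverse patterns.
- **The expected on-drug collapse in basophil activation is not evidence of inflation.** Collapse is the drug effect, so it cannot describe the null. With no effect, Visit 2 is an ordinary repeat measurement, and with correlation decaying over time the pooled test is conservative. This also stands: inflation is possible, not expected.
- **The effect may be large.** The ibrutinib study in section 1.3 found a 77% reduction in wheal area. At 1.5 SD or more little power is lost, though the documents cannot confirm such an effect for this drug.
- **The omnibus test is not weaker in the expected pattern.** It has 86.0% against 80.3% if Visit 3 returns fully to baseline. No document predicts a shift at Visit 3 alone.
- **Visit 3 is a planned assessment,** and protocol 10.3 compares each patient with baseline at every time point. Analysing it is legitimate. What remains is that it should not form part of the efficacy test.

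**Conclusion.** The point holds in a limited form. The planned test for the skin-test and basophil endpoints does not match their question: it includes an off-drug visit and leaves the relevant contrast unnamed. A significant F is not by itself evidence of a drug effect; under a 1-SD shift at Visit 3 alone (n = 10, correlation 0.5) it rejects about 86% of the time.

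At an assumed 1-SD change, corrected follow-up tests have 60-70% power for three comparisons or 68-76% for two, against 80% for the single paired contrast. The loss is small at 1.5 SD.

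A claim that the plan inflates false positives in general would go too far. Inflation needs Visit 2 to be the more variable or less correlated visit and no correction. It is absent under sphericity, and the pooled contrast turns conservative if Visit 3 is the noisier visit. All sizes rest on assumed effect sizes and correlations, because the documents give none for these endpoints.

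Severity is low. The endpoints are secondary, the SAP also plans descriptive statistics, and the primary analysis is unaffected. This is a cheap improvement.

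**What to change.** In the SAP's Data Analysis section:

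- Name the paired Visit 2 minus Visit 1 comparison, using the SD of that difference, at two-sided 0.05 as the test for each secondary endpoint. Name the paired non-parametric substitute and when it applies.
- Report Visit 3 versus Visit 1 separately, as recovery after stopping the drug.
- If the three-visit ANOVA is kept as support, apply the Greenhouse-Geisser correction and say which comparisons form the family for Šídák or Bonferroni.

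The cost is SAP wording only, with no added subjects, visits or procedures. The statistical price is about 6 points of power relative to the omnibus test alone (86.0% − 80.3% = 5.7) if Visit 3 returns exactly to baseline. If Visit 3 returns only half-way, the paired contrast is ahead by about the same margin (80.3% − 74.2% = 6.1).
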